1.1 Overview and Objective

The glucose profile of normal healthy children has not been well described over a 24h period. The characterization of the glucose values in normal children during day and nighttime is critical to the interpretation of glucose values in pathological states, such as diabetes. This is particularly important in analyzing the levels of low glucose values overnight observed in diabetic children. As a first step, we will conduct a pilot study to determine whether continuous glucose monitors measuring subcutaneous fluid glucose levels are sufficiently accurate to use for this purpose. There are two continuous glucose monitors, the GlucoWatch® biographer (GW biographer) and the Continuous Glucose Monitoring System® (CGMS), that are FDA-approved for use in patients with diabetes. A study is presently being conducted by our group looking at the accuracy of these monitors in children with diabetes comparing the results obtained with these monitors against the gold standard blood glucose measurements. If these monitors are found to be sufficiently accurate, then their use provides the opportunity to assess glucose values in normal children as they go about usual daily activities in the home environment. However, the assessment of the variation of blood glucose concentrations in normal children as well as how well these numbers correlate with those obtained using the continuous glucose sensors will necessitate first an inpatient study to measure blood glucose at frequent regular intervals over a 24-hour period using both the continuous glucose sensors (CGMS and GW biographer) as well as the gold standard blood sugar.

At one of the DirecNet centers (Yale University), the CGMS was used by 31 normal children in the home environment (unpublished). Twenty-seven of the 31 children had at least one glucose value <60 mg/dl during up to 72 hours of sensor use. Eighteen children had at least 30 minutes of sensor values <60 mg/dl, primarily overnight, during the first 24 hours of sensor use. For some of the children, the duration of the nocturnal low glucose levels was two or more hours. Additional anecdotal information of normal subjects wearing the continuous glucose sensor having frank hypoglycemic values also abound. Whether these decrements in glucose concentrations are real or whether they represent an inherent analytical issue with this instrumentation remains to be elucidated.

1.2 Synopsis of Study Design

At five clinical centers, a pilot study will be conducted on 20 healthy subjects (7 to <18 years old) who do not have type 1 or type 2 diabetes nor history of the disease in the immediate family. Each subject will be hospitalized for approximately 26 hours to assess the accuracy of the continuous glucose monitors compared with 'gold standard' blood glucose measurements. The data will be evaluated after the first 10 subjects to determine whether any modifications in the protocol should be considered for the second 10 subjects.

During the hospitalization, each subject will simultaneously use both the GW biographer and CGMS sensors and have blood drawn for gold-standard blood glucose measurements every 60 minutes during the day and every 30 minutes overnight.

1.3 Background Information on the GlucoWatch Biographer

The GlucoWatch biographer was developed and is distributed by Cygnus, Inc. It looks like a watch and is worn on the forearm, three or more inches from the wrist or elbow joint.¹ An adhesive pad incorporating two hydrogel discs attaches the device to the skin. Each disc is the size of a dime. A triple 'A' battery from the biographer sends a small current through the discs to pull glucose from

the interstitial fluid underneath the skin. The glucose in the interstitial fluid is then measured. The maximal current used is very small (that of the triple 'A' battery). Each cycle lasts for 20 minutes.

The biographer model to be used in the study (GlucoWatch 2 biographer) gives up to 6 readings per hour, for 13 hours. The subjects can read glucose values displayed on the biographer. It also has a high and low glucose alarm that can be set by the user for certain glucose levels of their choice (e.g., less than 70 mg/dl and/or more than 300 mg/dl). A two-hour warm-up time followed by a single glucose meter value is needed to calibrate the device. The GlucoWatch 2 biographer is the identical mechanical device as the GlucoWatch biographer, but the software has been changed to allow for a 2-hour instead of a 3-hour warm up, and readings are made every 10 minutes instead of every 20 minutes. This device will not require an IDE. The biographer can be affected by the following:

- Sweat. There are two small metal bars on the bottom side of the GlucoWatch biographer that measure how much sweat is on the skin. If excessive sweating is detected, the cycle will be skipped (i.e. no value given for that 10-minute period).
- Temperature. If the temperature or rate of change in temperature is beyond a pre-programmed level, the cycle will be skipped.
- Glucose values outside the range of 40-400 mg/dl are just read as either LOW or HIGH.

Subjects wearing the GlucoWatch biographer may develop erythema and a localized skin reaction to the adhesive used to secure the GlucoWatch biographer to the skin, or to the hydrogel iontophoresis pads. Very rarely a severe skin reaction could result in scarring.

The Food and Drug Administration (FDA) has approved the GlucoWatch biographer for adults, and data have been submitted to the FDA requesting its approval for children. Although the accuracy of the device has been demonstrated,¹⁻⁶ the FDA approval does not allow for immediate changes in therapy (such as insulin dosing) to be based solely on the biographer values. All treatments and changes to insulin dosages during this study will be made using only the meter values and not the biographer values.

1.4 Background Information on the Continuous Glucose Monitoring System

The CGMS was developed and is distributed by Medtronic Minimed, Inc.⁷ This sensor uses a glucose oxidase based electrochemical sensor which generates 2 electrons for each glucose molecule oxidized. The current generated from measuring glucose is called the ISIG (Input SIGnal). The CGMS system is designed to measure blood glucose levels in a range of 40-400 mg/dl. The sensor is inserted subcutaneously and measures interstitial glucose. Lag times between changes in the serum glucose and changes in sensor output are generally between 4 and 9 minutes in animal studies.⁸ In human studies the interstitial glucose levels generally lag behind the blood glucose by 3 to 13 minutes.^{9,10} When functioning properly, the CGMS acquires glucose values every 10 seconds and these values are averaged in the monitor to provide a reading every 5 minutes (or 288 readings a day). Each sensor is designed to measure readings for 24 to 72 hours; many sensors will not function for a full 72 hours. The sensor can be inserted with equal success by patients and health care professionals, has been able to work in a broad age range (from 2 weeks to 74 years old), and sex, race and duration of diabetes do not appear to influence sensor function.^{11,12} The sensor is well tolerated with the only side effect being mild to moderate site irritation in 2% of patients.¹¹

The present version of the CGMS, which has been approved by the FDA, provides data in a retrospective analysis, much like a Holter monitor. The sensor does not display the glucose in "real

time” and does not have alarms to warn of hypoglycemia or hyperglycemia. The sensor requires at least 3 capillary glucose readings each day to validate sensor function and allow for development of a calibration equation. These calibration measurements are performed with a home glucose meter, and calibration is dependent upon the subject entering glucose values correctly into the sensor. The sensor cannot be worn in the water and must be kept dry. There are several reasons for sensor “failure”: 1) A faulty connection between the sensor and the connecting cable will cause frequent “disconnect” warnings. This problem can be avoided by careful insertion of the cable into the sensor, with the sensor and the cable connection maintained in a flat, horizontal plane at the time of connection. 2) The sensor becomes “fouled.”

CHAPTER 2

SUBJECT ELIGIBILITY AND ENROLLMENT

2.1 Study Population

Up to 20 healthy subjects will be enrolled in this study at five clinical centers with approximately equal numbers enrolled at each center.

Enrollment will include approximately 10 subjects in each of the age groups of 7.0 to <12.0 years old and 12.0 to <18.0 years old.

Subjects will include both males and females and an enrollment goal will be to achieve an equal sex distribution in each age group.

A goal of recruitment will be to enroll a minimum of 3 African-Americans.

2.2 Eligibility and Exclusion Criteria

2.2.1 Eligibility

To be eligible for the study, a subject must meet the following criteria:

- 1) Age 7.0 to less than 18.0 years
- 2) Weigh at least 16.0 kg
- 3) Body mass index (BMI) between the 10th to 90th percentile for age and sex (based on CDC, 2000 nomogram)
- 4) Normal HbA1c (<6.0 with the DCA2000)
- 5) Normal hematocrit (according to normal range at the clinical center's lab)
- 6) Parent/guardian and subject understand the study protocol and agree to comply with it
- 7) Informed Consent Form signed by the parent/guardian and Child Assent Form signed by the subject

2.2.2 Exclusion

Subjects who meet any of the following criteria are not eligible for the study:

- 1) Family history of type 1 or type 2 diabetes in a sibling or parent
- 2) History of diabetes or positive islet cell antibody testing
- 3) The presence of skin abnormalities or significant medical disorder that in the judgment of the investigator will affect the wearing of the sensors or the completion of any of the protocol testing specified for the subject's age and weight.
- 4) Use of any medications (prescription or nonprescription) in the 7 days prior to CRC admission

2.3 Patient Enrollment and Baseline Data Collection

Potential subjects will be evaluated for study eligibility through the elicitation of a medical history and performance of a physical examination by a study investigator.

2.3.1 Informed Consent

For eligible subjects, the study will be discussed with the subject and parent/legal guardian. The parent will be provided with the Informed Consent Form to read and will be given the opportunity to ask questions. The subject will either be given the Child Assent to read or it will be read to the

child. If the parent and child agree to participation, the Informed Consent Form and Child Assent Form will be signed and the inpatient hospital stay will be scheduled.

2.3.2 Historical Information

A history will be elicited from the subject and parent and extracted from available medical records. Data to be collected will include: age, gender, race, history of diabetes in family members, chronic medical conditions, medications being used, and medication allergies.

2.3.3 Physical Exam

A standard physical exam (including vital signs and height and weight measurements) will be performed by the study investigator or his or her designee (a pediatric endocrinologist, pediatric endocrine fellow, or a pediatric endocrine nurse practitioner). The physical exam will include inspection of the skin (with particular attention to rashes, eczema, sun burn, and lipohypertrophy), and Tanner staging of breast and pubic hair in females and genital development and pubic hair in males.

2.3.4 Laboratory Tests

1. Hemoglobin A1c (using the DCA2000)
2. Hematocrit (using whatever method is in standard use at the center)

These can be measured either during an office visit within two weeks prior to admission or at the time of admission to the CRC.

If either the HbA1c or hematocrit is measured at the time of hospital admission, no gold standard blood draws will be done until the results are available and verified to be in the normal range.

CHAPTER 3

INPATIENT STUDY PROCEDURES AND MANAGEMENT

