3.1 Overview

On admission to the CRC, (1) a GW biographer will be placed, (2) a CGMS inserted, and (3) an intravenous catheter inserted for the gold standard glucose measurements. Subjects will be in the CRC for approximately 26 hours.

The inpatient procedures are summarized below and detailed in subsequent sections.

The study will consist of the following:

- 1) Gold standard blood glucose measurements will be hourly during the day and every half hour overnight.
- 2) The accuracy of the CGMS sensor will be assessed for approximately 24 hours. Simultaneous use of a second CGMS sensor during the inpatient stay will be optional.
- 3) The accuracy of the GW biographer will be assessed over approximately 24 hours of use, with a minimum of a 2-hour period of time where the use of two biographers will overlap.

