3.2 Sensor Management and Procedures

3.2.1 GlucoWatch Biographer

The second generation device will be used for these studies. Subjects will wear the biographer on the forearm or upper arm. The time of placement and the placement site of each biographer will be recorded (right or left arm, inner or outer arm, forearm or upper arm). An assessment will be made of the skin in the area of sensor placement. The biographer alarm settings will be set to be 40 mg/dl (low) and 400 mg/dl (high).

The first biographer (GWB#1) will be placed at the time of admission and calibrated two hours later. The second biographer (GWB#2) will be placed after GWB#1 is calibrated and no later than 9 hours after GWB#1 is calibrated, with its calibration completed two hours later. Assuming that GWB#1 does not prematurely shut off without being replaced, there will be at least two hours of overlap between the two biographers. If the timing of placement of GWB#2 is such that it will be removed prior to the end of the 24 hours of gold standard measurements, then GWB#1 will be used a second time with a second sensor (placed coincidentally with removal of the first GWB#1 sensor and calibrated two hours later). If GWB#2 sensor is removed 4 or more hours prior to the last 24-hour gold standard measurement, then a second GWB#2 sensor can be placed at investigator discretion. A sensor may be removed and replaced with a new sensor prior to the end of 15 hours if necessary to avoid having to place a new sensor overnight while the subject will be asleep.

Calibration glucose values will be obtained with the study HGM using venous blood obtained at the time of a gold standard blood draw. After the initial calibration, additional calibrations will be performed when the required CGMS calibrations are performed.

Prior to hospital discharge, a skin assessment will be made by two observers for all areas where a biographer was worn. Both erythema and edema will be scored on a 0 to 4 scale (as described on the case report form and in the Procedures Manual). If the sum of the erythema score and the edema score is 6 or greater, an Adverse Event Form will be completed.

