6.3 Subject Withdrawal

Participation in the study is voluntary, and a subject may withdraw at any time.

The investigator may withdraw a subject who is not complying with the protocol.

A subject who is enrolled but at the time of CRC admission is found to have an abnormal HbA1c or hematocrit will be withdrawn. An enrolled subject who at the time of CRC admission reports having used a systemic medication (prescription or nonprescription) in the prior 7 days will either be rescheduled or withdrawn.

A subject who is unable to use the sensors will be withdrawn and will not be counted towards the recruitment goal when he or she is unable to successfully use at least one CGMS and one biographer for 12 hours as an inpatient.

Subjects who withdraw or are withdrawn from the study without completing at least 12 hours of sensor use will be replaced if the full cohort has not yet been recruited at the time the subject is withdrawn from the study.

Subjects who are admitted to the CRC and have at least one gold standard blood measurement will receive payment for the inpatient stay even if withdrawn prior to completion of the study.

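### When HbA1c or hematocrit is first tested at admission, only the gold standard draws are held, so both sensors and the catheter can be placed in a child not yet known to be eligible (minor)

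*Protocol*

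**What the plan says.** Protocol 2.2.1 lists a normal HbA1c (item 4) and a normal hematocrit (item 5) among the eligibility criteria. On when they are tested, 2.3.4 says: "These can be measured either during an office visit within two weeks prior to admission or at the time of admission to the CRC". Where one of the two tests is done at admission, the same section adds that "no gold standard blood draws will be done until the results are available and verified to be in the normal range". No other procedure is held.

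The admission sequence is in 3.1: "On admission to the CRC, (1) a GW biographer will be placed, (2) a CGMS inserted, and (3) an intravenous catheter inserted". Section 3.2.1 repeats it for the first biographer: "The first biographer (GWB#1) will be placed at the time of admission and calibrated two hours later". Neither section refers to the laboratory results.

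Section 6.3 foresees a failed test at this stage: "A subject who is enrolled but at the time of CRC admission is found to have an abnormal HbA1c or hematocrit will be withdrawn".

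Three timing rules also bear on the point:
- Section 3.3 puts the first gold standard draw on the first whole hour that falls an hour or more after CGMS insertion.
- Sections 3.2.1 and 3.2.2 take calibration blood for both devices at a gold standard draw.
- Section 3.3.1 allows for extra draws for biographer calibration.

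**The concern.** The hold protects against the blood draws but not against the device and catheter procedures that come before them. A child tested at admission can have a biographer running, a subcutaneous sensor inserted and a venous catheter in place, then be found ineligible and withdrawn.

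The subjects are healthy children, and 6.1 states that they gain no direct benefit. The protocol's own risk text names skin irritation with, very rarely, scarring (1.3), severe irritation as a potential risk (5.5.1) and a low risk of local infection at the CGMS site (5.5.2). For a child who is then withdrawn as ineligible, that exposure serves no purpose of the study and could have been avoided.

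There is a second, weaker strand. The hold is not tied to the rules that start the draw series and the first biographer calibration, so the text does not say what follows if a result comes late.

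**Working it through.** **Step 1. Does the text really allow devices before results?** Set 2.3.4 beside 3.3. The first gold standard draw already comes at least 1 h after CGMS insertion. If insertion waited for verified results, every draw would follow the results automatically and the hold would be redundant. The hold therefore matters mainly when the CGMS is already in while results are pending. Placement before results is the natural reading of 2.3.4 with 3.1 and 3.2.1, not a strained one.

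**Step 2. Reproduce the plan's draw count.** From 3.3.1: 24 hourly + 10 half-hourly = 34 draws. Check by volume: 10.2 ml / 0.3 ml = 34, and 44.2 ml / 1.3 ml = 34. The figure reproduces exactly, so one draw is 1/34 = 2.9% of the series.

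**Step 3. How many draws can a late result displace?** Let the CGMS go in at *m* minutes past an hour (0 to 59), and let results arrive *T* hours after insertion.
- Scheduled first draw: F = m/60 + 1, rounded up to the whole hour.
- Held first draw: the later of F and (m/60 + T), the latter rounded up to the whole hour.
- Draws displaced: held first draw minus F, assuming the delay falls in the hourly daytime schedule.

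The protocol gives no turnaround time. *T* is an assumption, ranged from 0.25 to 4 h.

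| T after CGMS insertion | Draws displaced | Share of 34 |
|---|---|---|
| 0.25, 0.5 or 1 h | 0 | 0% |
| 1.5 h | 0 or 1 | at most 2.9% |
| 2 h | 1 | 2.9% |
| 3 h | 2 | 5.9% |
| 4 h | 3 | 8.8% |

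Example: with insertion at 9:40, the first draw is due at 11:00. With T = 1.5 h the results arrive at 11:10, so the first draw moves to 12:00 and one draw is displaced. With insertion at 9:20 and the same T, results arrive at 10:50 and the 11:00 draw stands.

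**Step 4. Displaced or lost?** The stay is about 26 h and the series 24 h, a difference of 26 - 24 = 2 h. The protocol does not fix a clock time for the end of the series and gives the stay only approximately. A late start may therefore shift the series rather than shorten it. Displaced draws are lost only if the end does not move.

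**Step 5. First biographer calibration.** It is due two hours after placement at admission. A hold that ends within those two hours does not delay it. A longer hold delays it if the calibration blood must come from a gold standard draw, as 3.2.1 says.

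**The case against.** The strongest reply is that this is a disclosed operating choice with limited consequences. Children are evaluated by history and physical examination, and consent is signed, before the stay is scheduled (2.3, 2.3.1). Testing at an earlier office visit is already permitted. Section 6.3 anticipates the abnormal result. The hold spares an ineligible child the 34-draw series, which is the largest blood burden. The protocol describes CGMS site irritation as mild to moderate and occurring in 2% of patients (1.4). Nothing shows how many children would be tested at admission or how many would fail. All of this stands, and it limits the severity. It does not answer why placement is left outside the hold.

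Three stronger readings are tempting, and the document does not support them:
- A reader might infer that the hold necessarily cuts into the reference period. It does not: a hold of up to 1 h after CGMS insertion displaces nothing, and the end of the series is not fixed.
- A reader might infer that a pending result blocks both the first draw and the biographer calibration. Section 3.3.1 contemplates additional calibration draws and budgets four, while 2.3.4 names only gold standard draws. Because 3.2.1 ties calibration blood to a gold standard draw, the text is unclear, but it does not establish a block.
- A reader might infer from 6.3 that the withdrawn child goes unpaid. That section guarantees inpatient payment to those with at least one gold standard measurement. It does not say that others receive none.

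A practical objection also stands. The hematocrit method is left to each center. If it needs venous blood, barring the catheter outright until results arrive could add a needle stick.

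**Conclusion.** The point holds as a minor one of subject burden and sequencing. As written, a child whose HbA1c or hematocrit is first measured at admission can have both sensors and a catheter placed before two eligibility criteria are known. This rests on the text alone. The number of children affected cannot be estimated from the protocol; 20 is only an upper bound.

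The effect on the data is conditional and small. Over the assumed turnaround of 0.25 to 4 h, between 0 and 3 of 34 draws (0% to 8.8%) are displaced for an affected child, and lost only if the series end is held fixed. No effect on the accuracy estimates has been shown.

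**What to change.** Amend 2.3.4 so that, when either test is done at admission, the hold also covers placement of the biographer and the CGMS. It should cover the catheter too, unless the catheter is used to draw the eligibility sample. Add a cross-reference in 3.1 and 3.2.1 saying that placement follows confirmation of eligibility, and start the device and draw clocks once the results are verified. With that order no draw is displaced by the hold, and the calibration rule in 3.2.1 and the start rule in 3.3 need no exception.

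Alternatively, have both tests done at the office visit within two weeks before admission that 2.3.4 already allows.

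The cost is an amendment of wording and, under the first option, a somewhat later start for children tested at admission. Nothing changes for those tested beforehand. No endpoint, sample size or analysis is affected.
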